# I. Abstract

#### **State of the Problem**

In full arch implant rehabilitations, immediate loading is one of the advantageous aspects of these interventions. However, the conventional denture conversion technique is troublesome for both practitioner and the patient.

#### Aim of the Study

This article presents a smart digital approach to design and construct a screw retained immediately loaded full arch implant supported bridge based on the pre-treatment complete denture.

#### **Materials and Methods**

After intra oral scanning of the ridge form, implant positions, the denture is used to scan the intermaxillary relation and tooth positions and the fixed interim is designed and milled from PMMA. This technique is applicable when a single arch is treated or for bimaxillary implant rehabilitation cases. In this study 30 patients were grouped into two groups; group I in which a converted denture was made conventionally and Group II in which a converted denture was made digitally. General satisfaction, chair side working time, and esthetic outcome of the prostheses were recorded and quantified with a verbal rating scale following insertion of implant-supported prosthesis.

#### **II. Background**

Immediate implant loading has been a reliable procedure for rehabilitation of edentulous and prospective edentulous arches. It shortens the treatment time, reinstate esthetics, function, and endorses the patient acceptance to the treatment. ^{1,2}

Using a rigid material for construction of the immediately loaded fixed interim is an absolute requirement for the overall success of the treatment as it ensures splinting, cross arch stabilisation and proper force distribution.³⁻⁵ Denture conversion technique was proposed by Balshi and Wolfinger for provisionalization of full arch implant rehabilitation cases with success rate of 80%. Most of the failures were in the form of fractures of the converted dentures due to hollowing and the holes made in the denture to ensure passive seating and pickup of the titanium sleeve abutments using self-cure acrylic resin. These different material phases and compromised flange thickness are the main causes of fractures.^{6,9}

Using a highly cross-linked resins such as Polymethyle Methacrylate PMMA would reduce the incidences of interim fractures and thereby enhancing the success rate of the implant treatments.⁷

An alternative workflow for construction of the fixed interim requires impressions, model production, and jaw relation records then digitizing all these data then designing and milling the restoration. Fulfilling these steps is inconvenient and time consuming in addition to the limitations of the physical records.¹⁰ So, a digitalised workflow would be time and cost effective in such cases. However, acquisition of the ridge form, implant positions and jaw relation in edentulous patients are difficult and unpredictable. So, a modified workflow is presented in this article which is specifically tailored for immediate loading of full arch cases resulting in significant improvement of the treatment outcomes.

# **III. Research Question**

Will the digital conversion of the pre-treatment complete dentures in immediately loaded full arch implant cases, introduce a more time saving solution and better patient satisfaction?

Problem	the conventional denture conversion technique					
	is troublesome for both practitioner and the					
	patient					
Intervention	An alternative workflow for construction of					
	the fixed interim requires impressions, model					
	production, and jaw relation records then					
	digitizing all these data then designing and					
	milling the restoration.					
Comparator	A conventional denture conversion will be					
	done following the conventional fabrication					
	technique.					
Outcome	General satisfaction, chair side working time,					
	and esthetic outcome of the prostheses with a					
	verbal rating scale following insertion of					
	implant-supported prosthesis.					
Time of Follow-up	One week for fabrication of the denture					
	digitally, but no follow-up is needed.					
Study Settings	Removable Prosthodontics Department,					
	Faculty of Dentistry, Ain Shams University.					

#### IV. Aim of the Study Outcomes and Clinical Relevance

#### Aim

The objective of this study is to find out if a digitalised workflow will be time and cost effective when converting the pre-treatment complete denture into a screw retained immediately loaded full arch implant supported bridge.

#### Outcome

General satisfaction, chair side working time, and esthetic outcome of the prostheses with a verbal rating scale following insertion of implant-supported prosthesis.

#### **Clinical Relevance**

Providing proof for the use of a modified workflow which is specifically tailored for immediate loading of full arch cases resulting in significant improvement of the treatment outcomes.

#### V. Hypothesis

The null hypophysis considered for this study is that there will not be a significant statistic difference in patient satisfaction between the digitalized modified workflow presented in this article and the conventional one.

#### **IV. Ethical Considerations**

In this study each patient will be rehabilitated with a full arch implant supported prosthesis when immediate loading will be the chosen protocol in which a fixed interim prosthesis should be properly constructed after the conversion of a pretreatment complete denture either following the conventional fabrication technique or following the digitalized technique proposed.

• **Risks and Discomfort to Patients**: There are no serious risks regarding this study, however, mucosal irritation, slight pain, and discomfort are commonly related to conventional procedures during denture conversion.

• **Minimization of Risk:** mouth rinses and oral gel medications will be prescribed in case of mucosal irritation.

• Criteria for Discontinuation of Study or Enrollment or Modification of Intervention: In case of patient sickness, incompliance, or refusal to continue in treatment.

4

• Benefits to the Patients and to the Community: Digitized database for the patient's ridges, implant positions and intermaxillary relation will save time, and effort for both the dentist and the patient.

• **Privacy:** Privacy for participants is protected by several procedures, such as informed consent and transparency in how patient data is accumulated and analyzed. Data will be kept in a specific folder on a computer with passwords known only by the main operator.

• Confidentiality: Confidential data of the patients will be privately kept with the main operator.

• Data Management: Data will be saved in a specific folder with passwords known only by the main operator on his personal computer.

• **Consent Procedures if Applicable**: Before the provision of the treatments, each patient will read and sign a consent form supplied by the ethical committee of the Faculty of Dentistry, Ain Shams University, written in the Arabic language. The consent describes the steps of each procedure, their rights, and their role in the study. The consent will be kept with the main operator.

• Adverse Event Reporting: Any adverse reaction will be reported and written in the patients' data folder.

#### V. Study Design

This is a clinical cross over study.

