#### **Study Procedures**

#### 1. Sample Grouping

This study will comprise two equal groups of converted dentures based on their fabrication techniques in pateintes rehabilitated with a full arch implant supported prosthesis as follows:

**Group I**: fifteen dentures were converted conventially to be used as a fixed interim prosthesis for immediate loading.

**Group II**: fifteen dentures were converted digitally to be used as a fixed interim prosthesis for immediate loading.

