## 3. Clinical and Laboratory Procedures

For both groups, multiunit abutments will be inserted for each implant and secured to them according to the recommended torque. A small amount of putty rubber base will be mixed and

placed into the fitting surface of the pre-treatment denture, which then will be seated intraorally to mark the sites of the multiunit abutments. The denture will then be relieved over the marked sites until it was fully seated without interference.

For group I a conventional denture conversion will be made. For group II; the denture will be scanned extraorally using intraoral scanner. An intra oral scan will be made for the ridge form and multiunit abutments scan bodies and the scan will be extended to include the buccal and labial aspect of the ridge following the continuous scanning strategy.⁸

A scan of the opposing arch will be done then a large vent hole will be drilled in the denture, removing a portion of the flange and anterior teeth while maintaining the integrity of the lingual / palatal aspect to connect to the other side base and teeth. The denture will be inserted intraorally and the patient will be instructed to bite in centric occlusion to make an intra oral bite scan which records the exposed area of the ridge, the opposing arch, and the remaining portion of the denture. Alignment of scans will be done on Medit compare application. These scans will be exported to the design software and alignment will be done by a software as well, virtual alignment of all scans to each other will be performed except for the denture scan which will be loaded separately as a pre-operative wax up. On the aligned scans, multi-unit abutments scan bodies will be matched to the digital library scan bodies and virtual multiunit abutment analogues will be generated then, titanium sleeves abutments will be selected. Alignment of denture scan. Design of virtual gingiva will be made with flat fitting surface without overhangs or ridge lap parts. The screw access holes will be aligned and the area surrounding these channels will be thickened.

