# Questionnaire about patient satisfaction level with different techniques of denture conversion:

	Questions	0	1	2	3	4	5
1	How do you feel about the pleasure you get from food compared to						
	your complete denture?						
2	With respect to appearance, how satisfied are you with your fixed						
	restoration in comparison to your denture?						
3	With respect to speech, are you satisfied with your current fixed						
	prosthesis?						
4	How comfortable were you during the process of denture fixation?						
5	With respect to time, how satisfied are you with the process of						
	denture fixation?						

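### The protocol calls the study a crossover but describes two separate groups of 15 patients, and its visible text gives no rule for who receives which technique

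*Protocol*

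**What the plan says.** Section V, Study Design, is a single sentence: "This is a clinical cross over study". Sample Grouping says "This study will comprise two equal groups of converted dentures based on their fabrication techniques" and then lists fifteen dentures for each technique. The Abstract divides 30 patients between two groups, and Patient selection also plans for thirty patients. Ethical Considerations presents the two techniques as alternatives for each patient.

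Clinical and Laboratory Procedures gives each group its own procedure. The conventional arm gets one sentence, "For group I a conventional denture conversion will be made", and the digital workflow follows for Group II. The Statistical Analysis section compares the groups with the Mann-Whitney U test. In the Research Question table, the follow-up entry allows a week for making the denture "digitally, but no follow-up is needed".

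The visible text does not mention periods, sequences, washout, a second prosthesis for the same patient or a paired analysis. Nor does it mention randomisation, concealment or any other way of deciding who receives which technique.

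**The concern.** A crossover label tells the reader that each patient receives both techniques, so that stable differences between patients cancel. If each patient receives only one, that protection is absent and the comparison depends on how patients came to be in each group.

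The questionnaire gives a concrete route for imbalance. Two of its five items rate the new prosthesis against the patient's own old denture: item 1 on pleasure from food, and item 2 on appearance ("restoration in comparison to your denture"). If patients with poorer old dentures gather in one group, those items could favour that group whatever the technique. The Clinical Relevance section nevertheless promises proof. An analysis plan cannot repair this later, because allocation happens when patients are enrolled.

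**Working it through.** **1. Which design does the text describe?**

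- Crossover: the one sentence in Study Design.
- Two independent groups: the Abstract, Ethical Considerations, Sample Grouping, Patient selection, Clinical and Laboratory Procedures and Statistical Analysis.
- Use of the denture: in Group II "a large vent hole will be drilled in the denture, removing a portion of the flange and anterior teeth". The Background attributes fractures of conventionally converted dentures to "hollowing and the holes made in the denture". As written, one denture could not readily serve both techniques.

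**2. Reproducing the sample size.** Inputs from Sample Size Calculation: two-sided alpha 0.05, power 80%, d = 1.05, N = 30.

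Two independent groups, normal approximation:

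n per group = 2(z₀.₉₇₅ + z₀.₈₀)² / d² = 2(1.960 + 0.842)² / 1.05² = 2 × 7.849 / 1.1025 = 14.24, rounded up to 15, so N = 30.

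The plan's figure is reproduced. The exact noncentral t gives 79.3% power at 15 per group and 82.0% at 16. That small shortfall is not part of this point.

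**3. What a paired design would need.** The protocol gives no within-patient correlation ρ, so a range is assumed. With d on the between-patient SD, the paired effect size is d_z = d / √(2(1 − ρ)). Patients needed in total for 80% power (paired t-test):

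| Assumed ρ | d_z | Patients in total |
|---|---|---|
| 0 | 0.742 | 17 |
| 0.3 | 0.887 | 13 |
| 0.5 | 1.050 | 10 |
| 0.7 | 1.356 | 7 |

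If 1.05 were already the paired effect size, the answer would be 10. None of these comes near thirty patients.

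**4. What an imbalance could do (illustration only).** The document gives no size or direction for any imbalance, so the shifts are assumed. Setting: 15 per group, no technique effect, two-sided 5% Mann-Whitney test, 100,000 simulated trials per cell.

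| Score model | No shift | 0.3 SD | 0.5 SD |
|---|---|---|---|
| Normal, asymptotic test | 0.050 | 0.122 | 0.252 |
| Normal, exact test (U ≤ 64) | 0.045 | 0.113 | 0.237 |
| One 0–5 item (assumed mean 3.5, SD 1) | 0.047 | 0.115 | 0.231 |
| Total 0–25 (assumed mean 17.5, SD 4) | 0.048 | 0.119 | 0.250 |

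The false-positive rate is thus 11–12% at 0.3 SD and 23–25% at 0.5 SD.

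**The case against.** **The label does little harm in practice.** Grouping, N and test all follow a two-group design, so no wrong paired analysis is planned. This stands: N and the test do not need to change because of the label.

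**A crossover might still be meant.** Fifteen patients treated twice would also yield fifteen dentures per technique, and 15 lies within the 7–17 range above. But the Abstract and Patient selection both count thirty patients, and Ethical Considerations offers one technique or the other. The follow-up entry is weaker evidence, because the inclusion criteria ask patients to accept a follow-up programme. The case against a second period rests mainly on the absence of any mention of one.

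**The missing rule is an omission in an incomplete text.** Patient selection breaks off mid-sentence and one part of the document was not available, so the statement must stay limited to the visible text. Sample Grouping, where an allocation rule would naturally stand, is present and gives none.

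**The error rates use no input from the document.** True. They show sensitivity and are not an estimate of bias.

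A reader might infer more than the text supports:

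- *That the groups are biased.* Nothing in the document shows this.
- *That the mix of one-arch and two-arch cases confounds the comparison.* The Abstract says "This technique is applicable when a single arch is treated or for bimaxillary implant rehabilitation cases", but that describes where the technique can be used, not who is enrolled. Thirty patients and 15 + 15 = 30 dentures imply one arch each, and Ethical Considerations speaks of a single prosthesis per patient.
- *That chair-side time is more vulnerable than satisfaction.* Higher error rates for skewed times appear only if a constant is added to every time. With a proportional shift they are about 12% and 23%, no worse than for satisfaction.
- *That the study should simply be relabelled randomised.* The text never says that it is. That word may be used only if allocation really is random.

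**Conclusion.** The point holds in two parts. First, the crossover label is wrong as written: the operational sections describe two independent groups of 15 patients, and N = 30 matches the independent-group calculation, not a paired one at any assumed correlation from 0 to 0.7. Second, no patient is their own control and the visible text gives no assignment rule, so a difference between the groups cannot be credited to technique on design grounds alone.

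The possible size of the second part is unknown. The figures of about 12% and 25% rest entirely on assumed shifts of 0.3 and 0.5 SD. This is an inexpensive improvement to what the trial can conclude, and not evidence that its result will be wrong.

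**What to change.** In Study Design, replace the crossover wording with *two-arm parallel-group*. What follows depends on the state of the study, which the text leaves unclear: the Abstract, Sample Grouping and Methods of Evaluation use the past tense, while Ethical Considerations, Patient selection and Clinical and Laboratory Procedures use the future.

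- **If patients are still to be treated:** add to Sample Grouping *Patients will be allocated 1:1 (15 per technique) by a computer-generated random list, concealed from the operator until eligibility is confirmed*, and call the study randomised.
- **If treatment is complete:** describe the allocation actually used. If it was not random, label the study a non-randomised parallel-group comparison, report baseline case mix by group (including old-denture quality), and replace the promise of proof in Clinical Relevance with a statement of association.

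Cost: a short amendment and one list, with no extra patients or visits. The operator gives up the choice of technique, and a colleague must hold the list. If treatment is already complete, only the wording and reporting can change. Any selection risk from non-random assignment would then remain.

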#### **VI. Materials and Methods**

#### **Study Settings**

Faculty of Dentistry – Ain Shams University.

#### **Sample Size Calculation**

Sample size calculation was performed using G*Power version 3.1.9.7 based on the results of previous studies. A power analysis was designed to have adequate power to apply a two-sided statistical test of the null hypothesis that there is no difference between the tested items. By adopting an alpha level of (0.05) and a beta of (0.2), i.e., power =80% and an effect size (d) of (1.050) calculated based on the results of previous studies. (23,24) The predicted sample size (N) is (30), i.e., 15 samples per group (n = 15).

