#### 2. Patient selection

Thirty patients will be selected from the outpatient clinic of the Oral and Maxillofacial Prosthodontics Department, Faculty of Dentistry, Ain Shams

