# V. Statistical Analysis

The obtained data will be recorded, tabulated, and statistically analyzed using the Mann-Whitney U Test was used for comparison between the two groups. Statistics was done with IBM SPSS statistics v20. Data was presented as median and interquartile range.

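### The stated 80% power at 15 per group is not shown for the planned Mann-Whitney test: it is about 77% if the data are roughly normal (minor)

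*Protocol*

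**What the plan says.** Under Sample Size Calculation, the protocol sets a two-sided test, alpha 0.05, beta 0.2 (80% power) and "an effect size (d) of (1.050) calculated based on the results of previous studies. (23,24"). It names the software, G*Power, but neither the test nor a distribution. The result is "The predicted sample size (N) is (30), i.e., 15 samples per group (n = 15").

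The test appears later, under Statistical Analysis: "Mann-Whitney U Test was used for comparison between the two groups".

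Three other statements bear on the calculation:

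- **Outcome behind d.** The null hypothesis in the sample size section is "no difference between the tested items", while the Outcome section lists "General satisfaction, chair side working time, and esthetic outcome of the prostheses with a verbal rating scale". No outcome is attached to d.
- **Source of d.** The calculation cites references 23 and 24. The reference list ends at number 10.
- **Design.** Study Design says "This is a clinical cross over study". Sample Grouping says "This study will comprise two equal groups of converted dentures based on their fabrication techniques", and Patient selection says "Thirty patients will be selected from the outpatient clinic".

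**The concern.** A power statement should describe the test that will be used. Here the figure is stated in one section and the test in another, and nothing links them. A rank test generally does not have the same power as a t-test or a known-variance z-test at the same standardised difference, so the 80% needs checking against the Mann-Whitney test itself.

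At stake is whether the stated power can be relied on and whether a reader can verify it. Verification needs the outcome to which d = 1.05 belongs, its likely distribution and its source, and the protocol supplies none of these.

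**Working it through.** **Inputs.** All are from Sample Size Calculation except the test, which is from Statistical Analysis: two-sided alpha 0.05 (z = 1.960), power 80% (z = 0.842), d = 1.05, 15 per group, Mann-Whitney U test on two independent groups. No dropout allowance is stated, so it is taken as zero.

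**1. The protocol's own figure.** The known-SD normal approximation gives n per group = 2(1.960 + 0.842)²/1.05² = 14.24, so 15. By the same approximation, power at 15 is Φ(1.05·√7.5 − 1.960) = Φ(2.876 − 1.960), or 82.0%. N = 30 is reproduced.

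**2. The same formula adjusted for Mann-Whitney.** The asymptotic relative efficiency (ARE) against the t-test for normal data is 3/π = 0.955. Then 14.24/0.955 = 14.91, which also rounds up to 15.

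**3. Two-sample t-test (noncentral t).** With noncentrality 1.05·√(n/2), power is 79.3% at 15 and about 82% at 16. Strictly, 80% needs 16 per group.

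**4. Mann-Whitney, normal data, by ARE.** The effective n is 15 × 3/π = 14.32. The noncentral t with that n gives 77.3%. At 16 per group it gives 80.05%.

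**5. Mann-Whitney, normal data, by simulation (400,000 runs).**

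| n per group | Power |
|---|---|
| 15, large-sample test | 77.2% |
| 15, exact critical value | 75.8% |
| 16 | 79.0% |
| 17 | 82.1% |

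80% therefore needs 16 per group by ARE or 17 by simulation. Noether's formula gives 17.80, so 18. For 80% at 15 per group, d would have to be 1.060 by t-test or 1.087 by Mann-Whitney (normal data, ARE).

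**6. Other shapes, 15 per group, d = 1.05, simulated with the large-sample test.** The shapes are assumptions, because the protocol gives none.

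| Shape | Power |
|---|---|
| Uniform | 72.8% |
| Normal | 77.2% |
| Logistic | 81.1% |
| Laplace | 86.2% |
| Gamma, right-skewed (shape 8, 4, 2, 1) | 80.4%, 82.8%, 86.6%, 91.4% |

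With exact critical values the logistic case falls to 79.8%, so it lies at the boundary.

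**7. Ties on a rating scale (sensitivity only).** The protocol gives no scoring rule. If the five 0–5 questionnaire items were summed and generated from cut normal variables, power over 54 settings had a minimum of 76.1%, a median of 77.0% and a maximum of 81.5%; 53 of the 54 were below 80%. These scores are near-normal by construction.

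**8. Does the cross-over label explain 15?** If 1.05 were a paired effect size, a paired t-test would need 10 pairs (83.9%; 9 pairs give 78.8%). If it were instead scaled by the between-patient SD, the number of pairs would depend on the within-patient correlation: 17, 13, 10 and 6 at correlations of 0, 0.25, 0.5 and 0.75. Reaching 15 would need a particular low correlation, and the protocol states none.

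**The case against.** The strongest reply is that nothing has been shown to be miscalculated. N = 30 follows from the standard formula, and the usual Mann-Whitney adjustment to that formula also gives 15. The t-test is within one percentage point of 80%. The 77% rests on normality, which the protocol never claims; a plan that reports medians and interquartile ranges does not suggest it. Chair-side working time is a duration, for which right skew is plausible, and under such shapes the simulated power reaches 80% or more. Restating the power as 77% could then replace one unverified figure with another.

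Most of this stands. A reader might infer that the sample size is an arithmetic error or that only one formula can produce it; steps 1 and 2 rule out both. A reader might also infer that 80% is false for this trial. The documents do not support that either, since the answer turns on a distribution they do not give.

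Two things remain. The approximations that return 15 treat the SD as known, and direct simulation of the planned test with normal data still gives about 77%. The protocol also offers no other distribution, and no identifiable outcome or source for d, from which 80% could be confirmed. A separate statistical analysis plan may give more detail, but the power figure is asserted in the protocol, next to citations that its own list does not contain. Stating the assumption openly answers the worry about the replacement figure.

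**Conclusion.** The point holds as a minor one. At 15 per group and d = 1.05, the planned Mann-Whitney test has about 77% power for approximately normal data (75.8% with exact critical values), roughly 3 points below the stated 80%. For other shapes it may be lower (about 73%, uniform) or at or above 80% (logistic, Laplace, right-skewed). The stated 80% is therefore not met in the reference case and not shown otherwise.

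It would be tempting to conclude that the trial is underpowered. The shortfall is worth one or two patients per group under one assumed shape, which does not support that conclusion.

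The figures assume two independent groups of 15, no dropout and d = 1.05 taken at face value. The untraceable citations, the unnamed outcome and the conflict between a cross-over and two independent groups with an unpaired test are visible in the text whatever distribution is assumed.

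**What to change.** Keep N = 30 and the Mann-Whitney test, and replace the power statement with wording such as: *With 15 per group and two-sided alpha 0.05, power to detect d = 1.05 is about 77% by the planned Mann-Whitney test, assuming approximately normal data (about 79% by two-sample t-test); it may be lower or higher for other distributions.* If the sponsor has grounds for another distribution, state it and give the power that follows.

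In the same edit:

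- name the outcome to which d applies;
- correct the citations so that they point to entries in the reference list;
- reconcile the cross-over label under Study Design with the two groups of 15, the thirty patients and the unpaired test.

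If two independent groups are what is meant, the cost is wording only: a stated power about 3 points less favourable, no extra patients and no change of test. If a cross-over is really intended, the sample size and the unpaired test would both have to be worked out again.
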